Overall: Assessments will be made at Week 0 (Baseline) with follow-up visits every 4 weeks thereafter, for a total of up to 7 study related assessments (Week 0 (Baseline), Weeks 4, 8, 12, 16, 20 and Week 24 (Final Evaluation)). Subjects will return to the clinic for all follow-up assessments.

Baseline: Initial demographics and a brief medical history will be collected at Baseline from subjects or via chart abstraction after informed consent and after meeting all inclusion/exclusion criteria. Data on the primary endpoint will be collected: pressure ulcer size (stage, length, width, and depth) via clinician measurement with photographic documentation. Secondary endpoints of infection status of the ulcer including signs/symptoms of infection, amount and type of exudates, color and type of tissue/character of the wound bed and health care resource utilization (wound-related) and adverse events will also be collected at Baseline. The wound surface area (length x width), amount of exudate and tissue type will be recorded using the PUSH Tool 3.0, and a PUSH baseline score will be calculated (PUSH score).

Follow-up visits: Information collected at each follow up visit will include information on the pressure ulcer size (length, width, depth via clinician measurement with photographic documentation), PUSH sub-scores and total score, time to complete closure of wound, infection status of the ulcer including signs/symptoms of infection, health care resource utilization (wound-related) and adverse events. If applicable, reason for early discontinuation will be recorded. Treatment-related adverse events will be collected at all follow-up visits.

Procedures	Baseline	Follow-Ups	Final Evaluation
Study procedures			
Informed Consent and Privacy Authorization	X		
Inclusion/Exclusion Criteria	X		
Demographics			
Age, Race, Gender, Education, Insurance Status (from chart)	X		
Marital, Employment, Insurance Status			
Medical History			
Height, Weight, Smoking/Tobacco Status	X		
Spinal Cord Injury Information (from chart)	X		
Type of Bladder Management	X		
Number of Concomitant Ulcers	X	X	X
Use of Antibiotics	X	X	X
Primary efficacy endpoint			
Ulcer Depth, Length, Width, Stage	X	X	X
Secondary endpoints			
Wound Infection Status	X	X	X
Amount and Type of Exudate	X	X	X
Color/Type of Tissue/Character of Wound Bed	X	X	X
PUSH Scores	X	X	X
Health Care Resource Utilization (Wound-Related)		X	X
Safety			
Reason for Early Discontinuation (if applicable)		X	
Adverse Events	X	X	X

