
 – Patient has any wound that at enrollment is scheduled for surgical closure within 14 days – Use of any immunosuppressant medications (for example, cyclosporine, methylprednisolone, prednisone, methotrexate, alefacept, or infliximab) within 30 days of screening – Is unable to fully comply with the study requirements; for example, if the wound is in a place that the patient cannot reach him/herself and as such requires a caregiver to apply the study product, if the patient does not have consistent twice daily access to a caregiver, this patient would be ineligible for the study – Any condition or situation which, in the Investigator’s opinion, puts the subject at significant risk, could confound the study results, or may interfere significantly with the subject’s participation in the study – Patient is medically unstable or has a life expectancy of less than 12 months – Patient is pregnant – Patient is a woman of child-bearing potential and does not consent to or receive a screening urine pregnancy test prior to study enrollment – Current enrollment in an investigational drug or device study or participation in such a study within the last 30 days prior to Baseline (Week 0) 	

Name of Sponsor/Company:	Oculus Innovative Sciences, Inc.
Name of Finished Product:	Microcyn [®] Skin and Wound Care with preservatives (“Microcyn”)
Name of Active Ingredient:	N/A
Test Article, Dose, and Mode of Administration:	
Microcyn [®] Skin and Wound Care with preservatives, applied twice daily, topical administration	
Statistical Analyses:	
Efficacy Analyses:	
Efficacy will be tested via T-tests of percent change in wound size using an intention to treat (ITT) approach as well as a per protocol analysis. Secondary analyses will include Kaplan-Meier analysis to estimate time to complete wound closure, and may include linear and logistical regression to estimate the impact of patient characteristics on study endpoints, with special emphasis on variables that affect healing times, such as diabetes and smoking status. The efficacy population will include all patients entered into the study.	
Safety Analyses:	
Safety analyses will be conducted via Fischer’s exact tests, chi-square, and t-tests, as applicable. The safety population will include all subjects exposed to the any study product (Microcyn or saline) who have provided any post-treatment safety information.	
Sample Size Justification:	

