The numbers above represent “nodes” of care with nodes 1-4 representing the four basic components of an effective pressure ulcer care plan: (Node 1) necrotic tissue debridement; (Node 2) initial wound cleansing and repeated cleansing with each dressing change; (Node 3), prevention, diagnose and treatment of infection; and (Node 4), using a wet ulcer dressing that keeps surrounding tissue dry. Nodes 5-14 as shown above represent

assessment and reassessment of the healing strategy and its outcome(s) to ensure optimal healing.

Spinal cord injured patients are an especially vulnerable population for pressure ulcers because of both the immobility rendered by resultant paralysis and of impaired sensation. The National Spinal Cord Injury Statistical Center (NSCISC) estimates that between 231,000 and 311,000 Americans are living with a spinal cord injury (SCI), with approximately 12,000 new cases each year.⁴ As a result of increased research and interest, remarkable progress has been made in improving the quality of life and life expectancy for SCI patients. Secondary complications, however, continue to challenge individuals living with SCI and their caregivers. Pressure ulcers, in particular, “remain the single most important medical complication in terms of loss of time in educational or vocational pursuits, increased hospital stay and resulting financial expenditures.”⁵ In patients with paraplegia, pressure ulcers are the leading cause of rehospitalization;⁶ across injury levels, sepsis from pressure ulcers and genitourinary tract infections are the leading cause of death in Veterans with SCI.⁷

Recent cost estimates on treating pressure ulcers in SCI patients indicate a range of \$2,000 to \$70,000 per wound, with an annual aggregate cost of approximately \$2.2 to \$3.6 billion in the United States alone.⁸ In a retrospective study reviewing medical records of veterans with spinal cord injury, it was found that over 50% of pressure ulcers did not fully heal over the three-year study period, with over 70% of Stage IV ulcers remaining unhealed despite surgeries and multiple hospitalizations.⁹

⁴ *Spinal Cord Injury Facts and Figures at a Glance*, National Spinal Cord Injury Statistical Center, Birmingham, Alabama, February 2010, <https://www.nscisc.uab.edu>.

⁵ Jackson, AB., *Secondary Conditions of Spinal Cord Injury*, Spinal Cord Injury Network, <http://www.spinalcord.uab.edu/show.asp?durki=32106>.

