2. STUDY DESIGN

2.1. OVERALL DESIGN

2.1.1. STRUCTURE

This study is a randomized, open-label comparative study of Microcyn versus normal saline in the healing of Stage III and Stage IV pressure ulcers in subjects with spinal cord injuries.

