3.5.1. TIME TO WOUND CLOSURE

Time to wound closure will be defined as date from Baseline assessment to the date the patient reports the wound closed or the first time the wound is visually documented to be closed by the investigator at a study visit, whichever comes first. If the patient reports the wound to be closed between study visits, the investigator must confirm closure of the wound at the next study visit and note the exact date of wound closure, as reported by the patient, on the subject's clinic record.

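### Section 3.5.1 dates closure by patient report if there is one and by the next 4-weekly visit if not, so in this open-label trial any arm difference in reporting would shift estimated time to closure

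*Combined protocol and SAP*

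**What the plan says.** Section 3.5.1 runs time to closure from Baseline to "the date the patient reports the wound closed or the first time the wound is visually documented to be closed by the investigator", the latter "at a study visit, whichever comes first". When closure is reported before a visit is due, "the investigator must confirm closure of the wound at the next study visit". The date entered is then not the investigator's own, since the instruction is to "note the exact date of wound closure, as reported by the patient". The visit therefore verifies the closed state, while the date kept is the patient's.

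The synopsis sets a Baseline assessment "with follow-up visits every 4 weeks thereafter", up to Week 24. Section 3.3 allows 3 days either way. On blinding, Section 2.1.1 states: "This study is a randomized, open-label comparative study of Microcyn versus normal saline".

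Section 6.3.1 analyses time to closure by Kaplan-Meier as a secondary analysis. It also halts the study for success if, at the interim, estimated time to closure differs by at least 26% with p < 0.05. The plan provides no diary, no reporting schedule, no blinded assessor of closure, no interval-censored method and no sensitivity analysis on visit dates.

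**The concern.** The rule runs two clocks. A patient who reports closure between visits gets a date close to the event. A patient who does not report gets the date of the next visit, which can be 28 days later plus the visit window. Which clock applies depends on behaviour, and the patient knows the treatment. If one arm reports more readily, identical healing is recorded as faster healing in that arm. Confirmation removes reports of wounds still open at the next visit. It does not remove a report made too early on a wound that has closed by then; such a report keeps its early date.

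Time to closure bears directly on the faster-healing hypothesis in Section 1.4, and its estimate is one of the two conditions of the early-success rule. Section 3.5.1 is also loose about the patient's date: its first sentence can be read as the day of the report, its second as the closure day the patient states.

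**Working it through.** **Inputs from the documents.** 4-week visit interval; 24 weeks of follow-up; 80 subjects (a convenience sample, so there is no power figure to reproduce); an interim on at least 20 patients through Week 12; two-sided 5% tests.

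**Assumptions, not in the documents.** 1:1 allocation; no treatment effect; constant closure hazard; 30% to 90% closed by Week 24; accurate reported dates; no dropout; visits exactly 4 weeks apart; an unreported closure dated at the next visit.

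**Step 1: delay of an unreported closure.** If closure is spread evenly over the interval, the mean delay is 28/2 = 14 days. With a constant hazard λ = −ln(1−p)/24 per week, where p is closure by Week 24, it is 4 − [1/λ − 4e^(−4λ)/(1−e^(−4λ))] weeks. This gives 2.02, 2.04, 2.07 and 2.13 weeks for p = 30%, 50%, 70% and 90%.

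**Step 2: arm difference among patients who close.** Shift ≈ delay × (reporting share in arm 1 − reporting share in arm 2).
- 80% v 40%: 14 × 0.40 = 5.6 days.
- 100% v 0%: 14 × 1.00 = 14 days.

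**Step 3: simulated trials with no true effect** (2,000 per scenario; ranges over 30% to 90% closure). The last column is the log-rank false-positive rate in favour of the better-reporting arm (nominal 0.025).

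| Analysis | Reporting | Difference in mean among closers | False positives |
|---|---|---|---|
| N=80, Week 24 | 80% v 50% | 5-7% | 0.03-0.06 |
| N=80, Week 24 | 80% v 20% | 10-13% | 0.03-0.12 |
| N=80, Week 24 | 100% v 0% | 15-21% | 0.04-0.24 |
| N=20, Week 12 | 80% v 50% | 9-11% | 0.02-0.03 |
| N=20, Week 12 | 80% v 20% | 13-20% | 0.01-0.06 |
| N=20, Week 12 | 100% v 0% | 26-32% | 0.02-0.09 |

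The high false-positive rates need 90% closure. For N=80 at 30% to 50% closure, the rate is 0.028 to 0.040 across all three reporting patterns.

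**Step 4: effect on Kaplan-Meier summaries.** A Kaplan-Meier estimate also uses patients who have not closed, which dilutes the shift. Large-sample values at Week 24, with nobody reporting v everybody reporting:

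| Closure by Week 24 | Restricted mean (weeks) | Relative difference | Median (weeks) |
|---|---|---|---|
| 30% | 20.80 v 20.19 | 0.61/20.80 = 2.9% | not reached in either |
| 50% | 18.32 v 17.30 | 1.02/18.32 = 5.6% | 24 v 24 |
| 70% | 15.38 v 13.93 | 1.45/15.38 = 9.4% | 16.0 v 13.75 |
| 90% | 11.29 v 9.38 | 1.91/11.29 = 16.9% | 8.0 v 7.21 |

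At Week 12 the expected closure is 1 − √(1−p), which is 16%, 29% and 45% for p = 30%, 50% and 70%. A median would usually not be reached. With 20 patients that is about 3 to 9 closures in total.

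**Step 5: check of the remedy.** With both arms dated at visits (3,000 trials per scenario; 30% to 70% closure), mean times agree within about 0.1 week and the hazard ratio is 1.00 to 1.02. Two-sided rejection is 0.042 to 0.044 for N=80 and 0.025 to 0.050 for N=20.

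**The case against.** The strongest reply is that differential reporting is assumed. The documents give no evidence of it, and they suggest good knowledge of closure in both arms, because a patient or caregiver treats and re-dresses the wound twice daily. Section 3.5.1 can also be read to let a patient state at a visit a closure date that fell between visits. Few closures would then be visit-dated, though the dates would rest on recall. A well-kept patient date is more precise than a 4-week grid. All of this stands as a limit on likelihood. It does not secure equal reporting, because nothing in the plan requires patients to report or be asked for a date.

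A reader might infer that reporting alone could halt the study. The documents do not support that. The 26% figure is reached only at 100% v 0% reporting and only on a mean restricted to closers, whereas Section 6.3.1 names Kaplan-Meier and does not say which summary is compared. The rule also needs p < 0.05. Even at that extreme, this is met in favour of the better-reporting arm in about 2% to 9% of interim analyses.

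High closure rates are also doubtful. The Introduction cites a retrospective study of veterans with spinal cord injury in which over 50% of ulcers, and over 70% of Stage IV ulcers, did not fully heal over three years.

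Two further inferences go beyond the text:
- That dates would often be second-hand. The exclusion criterion about a case where "the wound is in a place that the patient cannot reach him/herself" is an example with no frequency, and a caregiver sees the wound more often than the clinic does. The Introduction calls these patients vulnerable to ulcers "because of both the immobility rendered by resultant paralysis and of impaired sensation", which says nothing about seeing closure.
- That this is the main secondary endpoint. No ranking is stated; the synopsis lists the PUSH score first and Section 1.3 lists time to closure first.

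**Conclusion.** The concern holds as a weakness in the dating rule, and nothing elsewhere in the documents corrects it. With no true effect, an arm difference in reporting moves mean time among closers by about 2 weeks times that difference: about 5.6 days at 80% v 40%, and about 14 days at the limit. On the restricted mean the shift is that amount times the proportion closed.

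The direction is unknown, since either arm might report more. The size rests on the assumed reporting shares, closure rates and accurate dates; premature reports are not modelled and could add to it. The shift is bounded by one visit interval per patient, and under accurate reporting it does not change who is counted as closed by Week 24. The primary endpoint, percent change in wound size, is unaffected. The change is worth making because it is cheap and protects the estimate used in the early-success rule, but the trial's main conclusion does not depend on it.

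**What to change.** In Sections 3.5.1 and 6.3.1, define the event in both arms as closure documented by the investigator, dated at the first scheduled visit at which the wound is documented closed. The synopsis allows the Final Evaluation to fall at complete closure, so a report may prompt an early visit. In that case, assign the next scheduled visit date, or treat the time as interval-censored between the last visit seen open and the first seen closed. Use this definition for the Kaplan-Meier analysis and for the early-success rule. Keep the patient-reported date, stated to be the day of closure rather than the day of the report, for a sensitivity analysis.

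No new data are needed. Closure times become coarser (a 4-week grid) and slightly longer in both arms, and the interval-censored option needs a method other than standard Kaplan-Meier. The change does not blind the judgement of closure, which stays with an investigator who knows the treatment. Reading the closure photographs blind to arm would address that separately.

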3.6. SCREEN FAILURES

A screen failure subject will be a person from whom informed consent is obtained and is documented in writing (i.e., subject signs an informed consent form) but who does not meet the study eligibility requirements.

3.7. PROTOCOL DEVIATIONS

This study will be conducted as described in this protocol, except for an emergency situation in which the protection, safety, and well-being of the subject requires immediate intervention, based on the judgment of the Investigator (or a responsible, appropriately trained professional designated by the Investigator). In the event of a significant deviation from the protocol due to an emergency, accident, or mistake, the Investigator or designee must contact Oculus at the earliest possible time by telephone. This will allow an early joint decision regarding the subject's continuation in the study. The Investigator will document this decision).

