3.2.5. DISCONTINUATION/WITHDRAWAL PROCEDURES

A subject may voluntarily withdraw from study participation at any time for any reason. If the subject withdraws consent and discontinues from the study, the Investigator will attempt to determine the reason for discontinuation and record the reason in the subject’s records. If a subject withdraws consent because of an AE, that AE should be indicated as the reason for withdrawal. In the event of early discontinuation, (i.e., prior to the earlier of complete wound closure or Week 24) and whenever possible, the subject should be asked to return to the study center to complete the final evaluations. Subjects who withdraw from the study will not be replaced.

If at any time during the study, the Investigator determines that it is not in the best interest of the subject to continue, the subject will be discontinued from participation. The Investigator can discontinue a subject at any time if medically necessary. The Investigator may discontinue a subject’s participation if the subject has failed to follow study procedures or to keep follow-up appointments. Appropriate documentation in the subject’s study record regarding the reason for discontinuation must be completed.

All subjects who fail to return to the study center for follow-up for any visit will be contacted by phone and/or email to determine the reason(s) why the subject failed to return for the necessary visit or elected to discontinue from the study. If a subject is unreachable

by telephone after a minimum of two documented attempts (one attempt on two different days), a registered letter (with duplicate sent by first class mail, postage prepaid) will be sent requesting that contact be made with the Investigator. Only after these attempts have failed will a subject be deemed lost to follow-up.

This study may be terminated in accordance with the Clinical Trial Agreement. Should this be necessary, both Oculus and the Investigator will ensure that proper study discontinuation procedures are completed.

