6.3. OVERALL STUDY EVALUATIONS AND MEASUREMENTS

6.3.1. EFFICACY

For the interim analysis, efficacy will be tested via T-tests of percent change in wound size using an intention to treat (ITT) approach as well as a per protocol analysis. For the final analysis, efficacy will be tested via T-tests of percent change in wound size using an intention to treat (ITT) approach as well as a per protocol analysis. Stratification of efficacy results by smoking status and study ulcer Stage will be conducted, although the results are expected to be similar given the stratified randomization.

For the interim analysis and final analyses, secondary analyses will include Kaplan-Meier analysis to estimate time to complete wound closure, and comparisons of infection status of the ulcer. Number and health care resource utilization (wound-related) will be tallied and compared between Microcyn and saline. Other secondary analyses may include linear and logistical regression to estimate the impact of patient characteristics on study endpoints, with special emphasis on variables that affect healing times, such as diabetes. If there are sufficient number of patients with multiple wounds, a mixed effects linear model

will be run, handling the patient as a group that has been randomized to a treatment to determine if there are any spillover effects of treating one wound with Microcyn.

If the interim analysis indicates that the difference in estimated time to complete wound closure between the two populations is 26% or higher at a significance level of $p < 0.05$, the study will be halted early for success.

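### Sections 3.7 and 3.2.5 let people who know the arm end a subject's study participation without criteria, so they can influence who has a Week 24 ulcer size

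*Combined protocol and SAP*

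**What the plan says.** Section 2.1.1 sets the design: "This study is a randomized, open-label comparative study of Microcyn versus normal saline". Nobody is masked.

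Two clauses allow a subject to be taken out of the study at discretion.

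- **Section 3.7 (sponsor and investigator together).** The trigger is narrow: "In the event of a significant deviation from the protocol due to an emergency, accident, or mistake". The investigator then calls the sponsor, and the reason given is: "This will allow an early joint decision regarding the" subject's continuation. The word significant is not defined and no decision criteria follow. The investigator documents the decision.
- **Section 3.2.5 (investigator alone).** The investigator may end participation where the subject "has failed to follow study procedures or to keep follow-up appointments". The clause is permissive and sets no threshold. The reason must be recorded.

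After early discontinuation, Section 3.2.5 adds that "whenever possible, the subject should be asked to return to the study center to complete the final evaluations". It does not provide for the remaining 4-weekly visits. It also states: "Subjects who withdraw from the study will not be replaced".

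For the analysis, Section 6.3.1 names "T-tests of percent change in wound size using an intention to treat (ITT) approach as well as a per protocol analysis". Section 6 gives no rule for a missing Week 24 size and no definition of the per-protocol set. Section 6.2 limits the efficacy population to subjects with Baseline and at least one follow-up visit, whereas the synopsis includes everyone entered.

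**The concern.** Both clauses act on study participation, not only on use of the product. The decision comes after randomisation and is made by people who know the arm and may know how the ulcer is progressing. Under Section 3.7, one of them is the sponsor. If removal is related to healing and differs between arms, the two groups with Week 24 sizes are no longer the groups that were randomised. The intention-to-treat label cannot supply sizes that were never taken. At stake are the false-positive rate and the size of the estimated effect on the primary endpoint. The per-protocol comparison is more exposed still, because its exclusions are undefined.

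**Working it through.** The plan has no power calculation to reproduce: the synopsis calls the 80 patients a convenience sample. The check therefore asks how far selective removal could move the planned test.

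**Inputs from the documents.** 80 subjects (synopsis), two-sided 5% level (Section 6.1), t-test of percent change in wound size (Section 6.3.1).

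**Assumptions.** Equal allocation, so n = 40 per arm (the ratio is not stated); outcome normal in SD units, higher meaning better healing; no true effect; k subjects removed from one arm only. Removal takes the k worst on a signal that correlates ρ with the Week 24 outcome. Neither k nor ρ is in the documents. Each case uses 40,000 simulated trials.

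**Case A: removed subjects are deleted from the analysis.**

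| k of 40 removed | ρ = 0.5 | ρ = 0.7 | ρ = 1 |
|---|---|---|---|
| 2 | 5.5% | 6.5% | 8.4% |
| 4 | 7.3% | 9.7% | 15.0% |

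With k = 4 the bias favours the arm with removals by 0.09, 0.13 and 0.19 SD. This can be checked by hand. If the four removed lie on average m SD below the mean on the signal, the bias is ρ × m × k/(n − k). The simulated 0.188 SD at ρ = 1 gives m = 0.188 × 36/4 = 1.69. At ρ = 0.5 the formula then gives 0.5 × 1.69 × 4/36 = 0.094 SD, which agrees.

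**Case B: the exit size stands in for the Week 24 size.** The exit size is treated as the signal itself, on the same scale as the final outcome. Removed subjects now contribute m instead of ρ × m, so the bias is (k/n) × (1 − ρ) × m, *against* the arm with removals.

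- ρ = 0.5: (4/40) × 0.5 × 1.69 = 0.085 SD, or about 0.09.
- ρ = 1: 0 SD.

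The simulated error rate with k = 4 is about 5% to 5.6%. With k = 2 (ρ from 0.5 to 0.9) it is 4.8% to 4.9%.

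**Reference points.** With nobody removed the error rate is 5.0% and the bias 0. Removal unrelated to outcome leaves the rate at 4.8% to 5.0%. With 40 per arm, 80% power is reached at about 0.63 SD, so a bias of 0.19 SD is 0.19/0.63 = 30% of that effect and 0.09 SD is 0.09/0.63 = 14%.

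Cases A and B differ in both size and direction, and Section 6 does not say which applies. Case B is also simplified: an exit size is taken earlier than Week 24, so a difference between arms in the timing of removal would add a distortion that it does not model.

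**The case against.** The case for leaving the text alone has real substance.

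- **The sponsor's role is limited.** A reader might infer that the sponsor helps decide on non-attending patients. It does not. The joint decision exists only in Section 3.7, for deviations due to emergency, accident or mistake. Removal under Section 3.2.5 is the investigator's alone. This stands.
- **Measurement does not simply stop.** Sizes up to removal exist and an exit evaluation is requested; the Final Evaluation column of Table 1 includes ulcer length, width and depth. This stands. What is lost is measurement between exit and Week 24.
- **Deletion is not the stated plan.** The analysis is labelled intention-to-treat, and Section 6.2 on its face excludes only those with no follow-up visit. The higher error rates apply only if removed subjects are dropped. This stands, and is why both cases are shown. But the plan does not adopt the exit size either.
- **Staff cannot simply pick the worst healers.** A deviation or non-adherence must come first, so ρ = 1 is an extreme. This stands.
- **Repeated sizes allow modelling.** Likelihood-based or imputation methods could use the 4-weekly data. They could, but they rest on untestable assumptions about why subjects were removed, and none is specified.
- **Removals are documented.** They can therefore be tabulated by arm. That makes an imbalance visible but does not restore the missing sizes.

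**Conclusion.** The point holds as a weakness of the protocol. Unmasked parties can, without criteria, end participation after a deviation, non-adherence or missed visits, and the plan then secures at most one exit size. With 4 of 40 removed from one arm and no true effect, the error rate is about 7% to 15% if those subjects are deleted (ρ from 0.5 to 1). It is about 5% to 6% if the exit size is used, with a bias of 0 to 0.09 SD the other way. These figures rest on assumed equal allocation, an assumed number of removals, removal in one arm only and an assumed correlation.

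A reader might go further and infer that selective removal is intended or has occurred, or that 15% is the expected error rate. The documents support neither. They show that the route is open, not that it was used, and 15% needs perfect foresight of the outcome together with deletion. The change is worth making because it is cheap and closes the route whichever analysis rule is adopted.

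**What to change.** Reword Sections 3.7 and 3.2.5 so that a deviation, non-adherence or a missed visit can affect only use of the study product, decided as now, and does not by itself end study measurement. Subjects who still consent and can attend keep the scheduled 4-weekly size measurements to Week 24 and are analysed in their assigned arm. Take the sponsor out of the decision on continued measurement. Report deviations and discontinuations, with reasons, by arm.

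Leave the best-interest and medical-necessity clauses of Section 3.2.5 to clinical judgement. Section 4 is a fixed rule that disenrols subjects who start a prohibited treatment; its wording must be reconciled with continued measurement.

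The rewording does not replace a rule for sizes that are still missing. Section 6 should state one and settle the difference between Section 6.2 and the synopsis on the efficacy population.

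The cost is protocol wording and, for probably few subjects, visits that are already on the schedule. Subjects who missed visits before will attend incompletely, so the gain is partial. Sizes measured off product may dilute the effect slightly, which is inherent in comparing subjects as randomised.
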